Graft Failure- Renal	90 consecutive days of dialysis dependency.				
Graft Failure-	Return to exogenous insulin therapy or initiation of oral hypoglycemic agents for greater				
Pancreas	than 30 days.				
Insulin	Insulin free.				
Independent					
Premature	A subject will be terminated prematurely from the study if: 1) the subject withdraws consent,				
Termination	2) is lost to follow-up, 3) the investigator or sponsor decision, 4) death, or 5) the subject is				
	found to have a positive TB test.				
Protocol Mandated	Any procedure performed solely for the purpose of this research study, not considered site				
Procedures	specific standard of care.				
Randomized	A subject who met all eligibility criteria; met with the study investigator or designee to				
	discuss the study purpose, requirements (i.e., time requirements, schedule of events, etc.),				
	discussed all risks and benefits, signed the informed consent document and was randomly				
	assigned to one of the two treatment groups.				
Reduced Follow Up	Randomized subjects who are no longer following the assigned study therapy regimen, and				
r i	do not meet the criteria for early termination, will continue to participate in the study for				
1	safety and applicable enupoint assessments.				
Renal Dysfunction	safety and applicable endpoint assessments. Two consecutive readings with an increase in serum creatinine of 25% from baseline.				

Clinical Trials in Organ Transplantation (CTOT) CONFIDENTIAL Protocol CTOT-15

Sensitizing Event	Defined as a blood transfusion, pregnancy, or an event in the opinion of the Investigator		
	would necessitate repeating the PRA.		
Treated Diabetes	Receipt of any oral medication or insulin for the treatment of diabetes for >14 days		
Tuberculosis	TB is defined as a positive TB Skin Test (TST/PPD) or a TB-specific interferon gamma release assay, such as a QuantiFERON®-TB, QuantiFERON®-TB in tube, or a T-Spot®.		
Withdrawn from Study Therapy	Subjects who prematurely discontinue study treatment will be treated according to the site specific standard of care and followed for safety until 52 weeks post-transplant.		
Primary Nonfunction (PNF)	Graft failure that occurs between 3 and 7 days post-transplant.		
Women of Child Bearing Potential (WOCBP)	WOCBP includes any female who has experienced menarche and who has not undergone successful surgical sterilization (hysterectomy, bilateral tubal ligation, or bilateral oophorectomy) or is not postmenopausal (defined as amenorrhea \geq 12 consecutive months; or women on hormone replacement therapy with documented serum follicle stimulating hormone level > 35 mIU/mL). Even women who are using oral, implanted, or injectable contraceptive hormones or mechanical products such as an intrauterine device or barrier methods (diaphragm, condoms, spermicides) to prevent pregnancy or practicing abstinence or where the partner is sterile (e.g., vasectomy), should be considered to be of child bearing potential.		
Humoral Rejection in Kidney	Defined as renal dysfunction, the presence of donor specific anti-HLA antibodies, and diffuse C4d staining as determined by a central pathologist		
Investigational Arm	 Induction: 5 day course of MEDROL® (methylprednisolone) or equivalent; Induction: Thymoglobulin® (Anti-Thymocyte Globulin- Rabbit); Maintenance Immunosuppression: NULOJIX® (belatacept); Maintenance Immunosuppression: Prograf® (tacrolimus), or generic; Maintenance Immunosuppression: CellCept® (mycophenolate mofetil- MMF), or Myfortic® (mycophenolate sodium), or generic. 		

Stage	GFR*	Description	Treatment stage
1	90+	Normal kidney function but urine findings or structural abnormalities or genetic trait point to kidney disease.	Observation, control of blood pressure.
2	60-89	Mildly reduced kidney function (as for stage 1) point to kidney disease.	Observation, control of blood pressure and risk factors.
3A	45-59	Moderately reduced kidney	Observation, control of blood
3B	30-44	function.	pressure and risk factors.
4	15-29	Severely reduced kidney function.	Planning for endstage renal failure.
5	<15 or on dialysis	Very severe, or endstage kidney failure (sometimes call established renal failure).	Treatment choices.

The Stages of	Chronic	Kidnev	Disease	(CKD)	
THE DIALES UP	CHIUMU	NULLEV	Discase	$\mathbf{C}\mathbf{N}\mathbf{D}\mathbf{I}$	

*All GFR values are normalized to an average surface area (size) of 1.73m².

Suffixes:

p suffix: the addition of **p** to a stage (e.g. 3A**p**, 4**p**) mans that there is a significant proteinuria.

T - the addition of T to a stage (e.g. 3AT) indicates that the patient has a renal transplant.

D - the addition of D to a stage 5 CDK (e.g. 5D) indicates that the patient is on dialysis.

1 ESSENTIAL STUDY COMPONENTS

1.1 Hypothesis/Research Question

This study will test the hypothesis that a NULOJIX® (belatacept) based regimen using Thymoglobulin® (Anti-thymocyte Globulin- Rabbit) induction as a means of minimizing and potentially withdrawing calcineurin inhibitors (CNI) will result in comparable rates of rejection and achieve superior renal function as compared with a tacrolimus-based maintenance immunosuppressive regimen in recipients of simultaneous pancreas and kidney transplants (SPK).

1.2 Primary Objective

The primary objective is to evaluate a NULOJIX® (belatacept) based regimen as a means of improving long term graft function without increasing the risks of immunologic graft injury by avoiding both CNI and corticosteroids.

1.3 Secondary Objective

The secondary objective is to evaluate whether a NULOJIX® (belatacept) based immunosuppression regimen with minimal exposure to CNIs achieves superior renal function, improves cardiovascular and metabolic risk profiles, and preserves protective immunity in recipients of SPK.

1.4 Primary Endpoint

The primary endpoint is mean glomerular filtration rate (GFR) calculated for each treatment group using the CKD-EPI equation at 52 weeks.

1.5 Secondary Endpoints

1.5.1 Measures of Renal Function and Injury

The following secondary endpoints will measure renal function and injury at week 52:

- 1. Proportion of subjects with eGFR < 60 mL/min/1.73 m2 measured by CKD-EPI.
- 2. Change in CKD stages from baseline.
- 3. Proportion of subjects with defined CKD stage 4 or 5.
- 4. Mean calculated eGFR using MDRD 4 variable model.
- 5. eGFR by CKD-EPI over time based on serum creatinine collected at all visits indicated on the Schedule of Events.
- 6. Incidence of successful discontinuation of tacrolimus in recipients randomized to the NULOJIX® (belatacept)t treatment arm (Investigational Arm)
- 7. The incidence of delayed graft function (*DGF- refer to study definitions page*).

1.5.2 Measures of Pancreatic Function and Injury

The following secondary endpoints will measure pancreatic function and injury at week 52, in addition to times of graft dysfunction:

- 1. Proportion of subjects with full pancreatic graft function (i.e., insulin independent).
- 2. Partial pancreatic graft function (i.e., fasting c-peptide levels ≥0.3ng.mL (0.1nmol.L), but requiring insulin or oral hypoglycemic agents).
- 3. Pancreatic loss (i.e., c-peptide value <0.3ng/mL).

1.5.3 Measures of Cardiovascular and Metabolic Parameters

The following will be measured at baseline, days 28, 84, and weeks 28, 36, and 52, unless otherwise stated below.

- 1. HbA1c.
- 2. Fasting Blood Sugar (FBS).
- 3. Standardized blood pressure measurement and use of anti-hypertensive medications.
- 4. Fasting lipid profile (Total Cholesterol, non-HDL Cholesterol, LDL, HDL, and triglyceride) and the use of lipid lowering medications at baseline, and weeks 28 and 52.

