For continuous outcomes, we will test for differences in response means among the treatment arms by fitting normal theory analysis of variance (ANOVA) or analysis of covariance (ANCOVA) models to the original scores or to some normalizing-variance stabilizing transformation of them. For some endpoints, these models may be fit separately by month post-randomization (i.e., time will be treated as a by-variable and no repeated measures analysis will be performed). Repeated measures models will be fit to HbA1c data and to the slopes of eGFR vs. time regressions. The latter will be estimated in a mixed effects repeated measures model in which both treatment-group means (with 95% confidence limits) of the individual subject slopes and the individual subject slopes themselves will be estimated and tested for equality. Distributions of the individual slopes will be examined graphically and compared among the treatment groups.

Response type	Response	Measurement Scale	Summary Statistics	Models to test for treatment effects
Primary Endpoint	Mean GFR at week 52 (based on CKD-EPI Eq.)	continuous	Mean and/or geometric mean + 95% CI	Mixed Effects Repeated Measures ANCOVA
	Week-36 LOCF for missing week-52 eGFR	continuous	Mean and/or geometric mean + 95% CI	Mixed Effects Repeated Measure ANCOVA
	Mean GFR at week 52 (based on CKD-EPI Eq.) For Completers	continuous	Mean and/or geometric mean + 95% CI	Mixed Effects Repeated Measure ANCOVA

Table 9. CTOT-15	primary and	secondary	clinical rest	ponse variables
	printing with	. Secondary	cillical ico	ounde vanached

Page 84 of 104

Response type	Response	Measurement	Summary	Models to test for
		Scale	Statistics	treatment effects
		ondary Endpoints	D II	x 1 1
Renal Function and Injury Endpoints	Indicator of week 52 eGFR<60 mL/min/1.7 m ² or day 85 - week 52 eGFR decrease < -10 mL/min/1.7 m ² (composite endpoint based on CKD-EPI Eq.)	dichotomous	Proportion + 95% CI	Log-binomial or Poisson regression
	Mean GFR at week 52 (based on week 52 MDRD4 values)	continuous	Mean and/or geometric mean + 95% CI	Mixed Effects Repeated Measure ANCOVA
	Slope of GFR vs. time Regression over day 85 – week 52, for each treatment arm	continuous	Slope Mean and Std. Error or mean + 95% CI	Mixed effects Repeated Measures ANCOVA
	Incidence of successful tacrolimus withdrawal	dichotomous	Proportion + 95% CI	Log-binomial or Poisson regression
	Incidence of dialysis at day 5	dichotomous	Proportion + 95% CI	Log-binomial or Poisson regression

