	Biopsy-confirmed Incidence of an increase of ≥ 1 CAN/IFTA grade, relative to baseline, at each follow-up assessment	Dichotomous (Banff score <1 vs. ≥ 1)	Proportion + 95% CI	Log-binomial or Poisson regression
	Prevalence of CAN/IFTA grades I, II, III at week 52	Dichotomous (1 outcome for each grade)	Proportion + 95% CI	Log-binomial or Poisson regression (1 model per grade)
Incidence and Severity of Rejection and Anti-donor reactivity	Incidence of Acute Rejection (AR) of renal or pancreatic transplant within the first 52 weeks	dichotomous	Proportion + 95% CI	Log-binomial or Poisson regression
	Banff score of the 1 st observed of renal or pancreatic AR within 52 weeks post- transplant	Ordered categories (3 levels)	Proportion + 95% CI	Proportional Odds model
	Highest Banff score observed within 52 weeks post-transplant for either renal or pancreatic transplant	Ordered categories (3 levels)	Proportion + 95% CI	Proportional Odds model

Page 85 of 104

Response type	Response	Measurement Scale	Summary Statistics	Models to test for treatment effects
	Steroid vs. nonsteroidal treatment for renal or pancreatic AR	dichotomous	Proportion + 95% CI	Log-binomial or Poisson regression
	Prevalence of anti- donor HLA antibodies at week 52 for renal or pancreatic transplant subjects	dichotomous	Proportion + 95% CI	Log-binomial or Poisson regression
Cardiovascular + Metabolic	Fasting blood sugar	continuous	Mean and/or geometric mean + 95% CI	Separate ANOVA or ANCOVA at weeks 28 and 52
	HbA1c (baseline through week 52)	continuous	Mean and/or geometric mean + 95% CI	Mixed effects Repeated Measures ANCOVA
	Blood pressure at weeks 28 and 52	Continuous	Mean and/or geometric mean + 95% CI at weeks 28 and 52	ANCOVA at weeks 28 and 52, with use of blood-pressure drugs as a covariate
	Use of BP medications	dichotomous	Proportion + 95% CI	Log-binomial or Poisson regression
	Fasting lipid profiles at weeks 28 and 52	Continuous	Mean and/or geometric mean + 95% CI	Separate ANOVA or ANCOVA at weeks 28 and 52
	Total daily pill count	continuous	Mean + 95% CI tabulated and plotted over time, by trt. group	Separate ANOVA or ANCOVA at day 85 and weeks 28 and 52 (or Poisson Reg)
Safety (for both renal and pancreatic transplant subjects)	Incidence of death or graft loss or undetectable C-peptide separately and as a composite	dichotomous	Proportion + 95% CI	Log-binomial or Poisson regression
	Incidence of any AE	dichotomous	Proportion + 95% CI	Log-binomial or Poisson regression

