Appendix 1: Schedule of Events – Pre-Transplant to Day 4 Post-Transplant (Visit 1)

Screening Assessments	Window
 Blood Type (A, B, O), Rh Factor HLA Typing (Class I: A, B, C, Class II: DR, DP, DQ) Peak PRA, Current PRA or cPRA (within 12 months prior to transplant), Crossmatch Hepatitis B, Hepatitis C, and HIV test results Last reported CMV (IgG, IgM and/or total CMV Ab) and EBV testing (IgG, IgM) Tuberculosis testing (within 12 months prior to transplant). If documentation is not present at the time of transplant, and the subject does not have any risk factors for TB, a TB-specific interferon gamma release assay (IGRA) may be performed. 	Retrospective data collection, no time limits unless specified. Repeat only if not available.
 Informed Consent and Assessment of Eligibility Demographics Medical History, Physical exam (BP, Pulse, Temperature, Respiration, Weight) Concomitant Medications Local Labs: Serum Pregnancy Test, Hematology Panel (CBC, differential, platelets), Chemistry 12-Panel / CKD-EPI equation, MDRD 4 variable, Serum Amylase, Serum Lipase, Fasting Lipid Panel (Total, HDL, LDL, Triglycerides), Hemoglobin A1c, Urinalysis 	Within 30 days prior to transplant, until time of transplant.
 Flow Cytometry (20mL blood in Cyto-Chex Tube) Intracellular Cytokine Staining – Viral Phenotyping (32mL blood in CPT Tube) Markers of Autoimmunity – PBMC (30mL blood in Green-top Tube) Markers of Autoimmunity – serum (5mL blood in Red-top Vacutainer) Gene Expression, mRNA profiling in blood (2.5 mL blood in PAXgene RNA tube) Cytokines and Growth Factors- serum (7mL blood in Red-Top Vacutainer) Serum Proteins – CTGF, TGFbeta (4.5mL blood in CTAD) Urine Proteins – CTGF, TGFbeta (supernatant) Gene Expression, mRNA profiling in urine (urine pellet) Non-HLA Ab, Anti-HLA Ab, DSA (5mL blood in Red-top Vacutainer) Genomics- gene polymorphisms (4mL in Lavender-top EDTA Vacutainer) Viral Monitoring by PCR (CMV, BKV, JCV, HHV6, HHV7) and Viral Assay Development (HHV3- varicella zoster, HHV6- roseola, HHV7- cofactor CMV, polyoma JC, WC, KI).(plasma from ICS sample) 	Within 48 hours prior to transplant
 Randomization (RhoRand System) Assessment of Events: AE/SAE Solumedrol®(Methylprednisone) : 500mg – Intraoperatively Thymoglobulin® (Anti-thymocyte Globulin – Rabbit) Prograf® (tacrolimus) CellCept® (mycophenolate mofetil) 	Day of Transplant
 Methylprednisolone 250 mg Thymoglobulin® (Anti-thymocyte Globulin – Rabbit) 	Day 1 Post-Transplant

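### Table 9 does not require adjustment for the pre-transplant values of blood pressure, lipids and HbA1c, and states no HbA1c contrast; this gives up precision but introduces no bias

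*Combined protocol and SAP*

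**What the plan says.** Section 1.5.3 sets the measurement times: "The following will be measured at baseline, days 28, 84, and weeks 28, 36, and 52, unless otherwise stated below". For lipids it narrows these, together with "use of lipid lowering medications at baseline, and weeks 28 and 52".

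Appendix 1 confirms that the pre-transplant values are collected. The visit 1 list includes "Physical exam (BP, Pulse, Temperature, Respiration, Weight") and "Fasting Lipid Panel (Total, HDL, LDL, Triglycerides), Hemoglobin A1c, Urinalysis", with the window "Within 30 days prior to transplant, until time of transplant".

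Table 9 in section 13.2.2 then gives the models:

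- **Fasting lipids:** "Separate ANOVA or ANCOVA at weeks 28 and 52". No covariate is named.
- **Blood pressure:** ANCOVA at weeks 28 and 52. The only covariate named is use of blood-pressure drugs.
- **HbA1c:** the response is "HbA1c (baseline through week 52"), in a mixed-effects repeated-measures ANCOVA. No covariate, contrast or constraint at baseline is given.

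The text of section 13.2.2 leaves the choice between ANOVA and ANCOVA open for continuous outcomes. It adds that for some endpoints the models may be fitted visit by visit, so that "time will be treated as a by-variable and no repeated measures analysis will be performed". Change from baseline in laboratory values appears in Table 9 only as a descriptive row with no model.

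Section 13.1 uses the word differently: in its list of assessment times for most secondary outcomes, it labels day 28 post-randomisation as baseline.

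**The concern.** The secondary objective (section 1.3) includes an improved cardiovascular and metabolic risk profile. The trial has 30 subjects per arm, and section 10.4.1 rules out stratified randomisation. A subject's own pre-transplant value is already in the database and can explain part of the variation in the later value. A plan that does not call for it accepts a larger standard error than necessary.

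Two details add to this. The HbA1c row puts baseline inside the response, so the quantity to be tested is unclear. And section 13.1 gives baseline a post-randomisation meaning, so an analyst told to adjust for baseline could pick the wrong value. Section 13.7 labels any analysis beyond the plan as ad hoc, so an adjustment that is not fixed in advance carries less weight.

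**Working it through.** **Inputs from the documents.** 30 per arm (section 13.3); secondary endpoints tested at 0.05 (section 13.3), taken as two-sided as in section 13.2.1; HbA1c at baseline and five later visits (section 1.5.3).

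**Inputs assumed.** The documents give no SD, effect size or correlation for blood pressure, lipids or HbA1c. I take a true difference of 0.7 SD, a little below the 12/16 = 0.75 SD in the first row of Table 11, and a range of baseline to week-52 correlations r.

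**Step 1: the plan's own power figures.** Table 11 concerns GFR but is the only power statement. A two-sample noncentral t calculation (58 df, 80% power) gives these detectable differences:

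| SD | alpha 0.05: computed / stated | alpha 0.10: computed / stated |
|---|---|---|
| 16 | 11.77 / 12.0 | 10.39 / 10.5 |
| 20 | 14.71 / 15.0 | 12.99 / 13.0 |
| 24 | 17.65 / 18.0 | 15.59 / 16.0 |

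Rounded up to the next half unit, all six agree. The same method is used below.

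**Step 2: week-52 comparison with and without the baseline covariate.** The unadjusted standard error is √(2/30) = 0.258 SD, so the noncentrality is 0.7/0.258 = 2.71 and power is 76%. Adjustment multiplies the standard error by √(1 − r²), with 57 df:

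| r | SE factor | SE (SD) | Variance removed | Power |
|---|---|---|---|---|
| none (unadjusted) | 1.00 | 0.258 | – | 76% |
| 0.2 | 0.98 | 0.253 | 4% | 78% |
| 0.3 | 0.95 | 0.246 | 9% | 80% |
| 0.5 | 0.87 | 0.224 | 25% | 87% |
| 0.6 | 0.80 | 0.207 | 36% | 91% |

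Estimating the slope inflates the standard error by about √(1 + 1/56) = 1.009, which costs less than one point of power.

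**Step 3: HbA1c.** Assume correlation 0.4 between baseline and each later visit, 0.6 between later visits, and an effect of 0.7 SD at all five later visits.

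- *Average over six visits including a pre-transplant value.* Effect (5/6) × 0.7 = 0.58 SD. Variance factor (6 + 2×5×0.4 + 2×10×0.6)/36 = 22/36 = 0.611. SE √(2/30 × 0.611) = 0.202. Power 81%.
- *Week-52 contrast, unadjusted.* Effect 0.7 SD, no dilution. Power 76%.
- *Week-52 contrast, baseline-adjusted.* SE 0.258 × √(1 − 0.16) = 0.237. Power about 83%.
- *Average over the five later visits, baseline-adjusted.* Variance factor (5 + 20×0.6)/25 − 0.16 = 0.52. SE 0.186. Power 96%.

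Dilution therefore appears in one of the four analyses, and only because a value that cannot differ by arm is averaged in.

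**Step 4: which baseline.** Section 1.5.3 lists baseline separately from day 28, and Appendix 1 places the values before transplant. Section 13.1 attaches the word to day 28. Under that meaning the HbA1c baseline is a post-randomisation outcome and the zero-difference argument fails. Adjusting for it could then remove part of the treatment effect.

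**The case against.** The best defence is that nothing here is wrong, only unspecified. Section 13.2.2 permits ANCOVA for continuous outcomes, and the lipid row does so expressly. An unadjusted comparison of randomised arms is unbiased and keeps its type I error, because chance baseline imbalance is already reflected in its standard error. These are secondary endpoints of a 60-subject phase II trial, and no power is claimed for them. All of that stands. It limits the point to precision and specification, but does not remove it: plain ANOVA complies with the lipid row, and the blood-pressure row names a covariate that is not the baseline value.

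A reader might infer that the HbA1c effect is diluted by design. The documents do not support this. Table 9 names no HbA1c contrast, and it uses the same model label for the primary endpoint, for which section 13.2.1 specifies a week-52 contrast. Nor is a baseline response an error in itself: with arm means constrained equal at baseline, the model is as efficient as ANCOVA.

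A reader might also set 81% against 96% and credit the difference to baseline adjustment of HbA1c. The 96% belongs to a five-visit average. The adjusted week-52 contrast gives about 83%.

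Finally, the correlations are assumptions. Subjects enter with c-peptide below 0.3 ng/mL and receive a pancreas, so pre-transplant HbA1c may predict the later value poorly. One range need not fit all three measures.

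**Conclusion.** The point holds as an inexpensive gain in precision and a gap in specification. Pre-transplant blood pressure, lipids and HbA1c are collected, and Table 9 requires adjustment for none of them. For a 0.7-SD difference with 30 per arm, the adjustment is worth about 2 to 15 points of power over assumed correlations of 0.2 to 0.6 (76% to between 78% and 91%). It is close to nothing if the correlation is lower, as it may be for HbA1c.

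The documents do not support saying that the plan forbids adjustment, that its comparisons are biased, or that the HbA1c effect will be diluted. Dilution from 0.7 to 0.58 SD is conditional on a test averaged over six visits with a pre-transplant value among them. The conflict between section 13.1 and section 1.5.3 with Appendix 1 over the meaning of baseline has to be settled first. The primary analysis and the sample size are unaffected.

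**What to change.** In Table 9 and the text of section 13.2.2:

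1. Define baseline for these outcomes as the last pre-transplant value from Appendix 1, and reconcile section 13.1, which labels day 28 as baseline.
2. Add that value as a covariate in the week-28 and week-52 models for blood pressure and for each lipid fraction.
3. For HbA1c, either use the pre-transplant value as a covariate, or keep it as a response with the two arm means constrained equal at baseline.
4. State the week-52 difference between arms as the tested HbA1c contrast.

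The cost is SAP wording and one degree of freedom per model. No new data are needed.

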1.5.4 Incidence and Severity of Rejection and Anti- Donor Reactivity

These endpoints will be assessed at 52 weeks post-transplant. Biopsy grading and antibody assessments will be performed at the CTOT-15 Core Laboratories.

- 1. The incidence and severity of acute cellular rejection defined by the Kidney Banff 2007 criteria and Pancreas Banff 2011 criteria within the first 52 weeks.
- 2. The severity of first and highest grade of acute cellular rejection in the renal and pancreas biopsies
- 3. The incidence of humoral rejection in the renal and pancreas biopsies.
- 4. The prevalence of *de novo* anti-donor antibodies and anti-HLA antibodies.
- 5. The type of treatment of rejection.

1.5.5 Safety Outcome Measures

The following safety outcome measures will be assessed:

- 1. The incidence of death, graft loss, or undetectable c-peptide.
- 2. The incidence of all adverse events (AEs) and serious adverse events (SAEs).
- 3. The incidence of selected AEs and SAEs including:
 - Infections requiring hospitalization or systemic therapy,
 - BK and CMV viremia (local center monitoring),
 - EBV Infection (local center monitoring),
 - Malignancy.

